Title	Can High-Intensity Interval Training (HIIT) reduce the risk of diabetes relapse following discharge from the NHS Path to Remission Programme? – a pilot study
Short title	HIIT post LCD
Chief Investigator	[name]
Objectives	To determine the effect of a 16-week home-based HIIT intervention on markers of glucose metabolism and glycaemic control in individuals with T2D that have achieved diabetes remission in the NHS Path to Remission Programme.
Trial Configuration	Parallel group, non-blinded, randomised control study
Setting	Clinical research facility (Postgraduate Centre, University of Nottingham, Derby Campus)
Sample size estimate	This is a pilot study, therefore no power calculation has been performed
Number of participants	20 participants will be recruited and allocated 1:1 into intervention or control groups
Eligibility criteria	
 • Adults between the age of 18-70 years • Ability to provide informed consent. • Completed the NHS Path to Remission programme and achieved diabetes remission (HbA1c <48mmol/mol (6.5%), and off diabetes medications for at least three months)
Description of interventions	The intervention group will participate in a 16-week HIIT programme involving 3 sessions per week in their own homes. The HIIT sessions are comprised of five 1-minute intervals of body-weight exercises interspersed with 90-second active recovery periods. The control group will continue with their usual levels of activity.
Duration of study	
Each participant will be involved in the study for 16 weeks.
 
The study is expected to commence in November 2024 and be completed by the end of August 2026.

Randomisation and blinding	Participants will be randomised to the two groups using the “sealed envelope” online software. Research staff in direct contact with participants will not be blinded, however staff involved solely in analysis of samples and data will be blinded to the randomisation of participants.
Outcome measures	
The primary endpoint for this study will be beta-cell function assessed during an intravenous glucose tolerance test (IVGTT)
 
Secondary outcome measures include:
 
 • Insulin sensitivity • Overall glycaemic control • Body weight • Body composition • Skeletal muscle function

	
 • Skeletal muscle structure • Cardiorespiratory fitness (measured as VO_{2max} during cardiopulmonary exercise testing, CPET)

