The intervention of this study will require participants to perform body-weight HIIT in their own home environment. Each participant's safety and suitability for engagement in such exercise will be assessed rigorously during the initial screening and baseline exercise testing. If any concerns become apparent at this stage then the participant will be removed from the study on the basis of their safety. Whilst exercising at home, participants will be provided with a list of concerning symptoms to be aware of, and advised to contact emergency services immediately if these symptoms were to develop. In addition, we will suggest to participants that they have another person in the near vicinity when performing their HIIT sessions – particularly for the initial sessions.

Stopping rules and discontinuation

The safety of participants is of utmost importance to our study group. Participants' continuation in the study would be deemed unsuitable if they were to develop any persistent, uncomfortable or clinically significant symptoms in response to any elements of the intervention(s) or procedures. Alongside the participants' right to withdraw from the study whenever they choose, the study team reserves the right to discontinue a participant's involvement if the Chief Investigator decides that continued involvement is not in their best interests. The basis of this decision will be discussed with the participant to achieve a mutually agreed outcome.

There are some criteria that would warrant immediate removal from the study, to ensure the safety of the participants in relation to the exercise element of this study. In particular, immediately removal will be considered if a participant were to develop any of the following symptoms during any exercise sessions (CPET or HIIT):

- Chest pain or tightness,
- Palpitations,
- Faintness,
- Sudden pallor,
- Loss of co-ordination,
- Confusion,
- Dizziness, or
- Excessive breathlessness

Participants will be given lay language information detailing these symptoms to ensure that they are aware of them at all times, especially when performing the HIIT sessions in their home environment.

In addition, as participants will be monitored during their CPET sessions, they will also be observed for the following signs:

- Changes on continuous ECG monitoring suggestive of ischaemia (e.g. >2mm ST depression) or arrhythmia
- Systolic blood pressure rising >250mmHg
- Diastolic blood pressure rising >120mmHg

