- Blood pressure drop of >20mmHg
- Drop in heart rate >10 beats per minute
- Oxygen saturations <94%

If any of these were to occur during the CPET session then this will also be grounds for removal from the study to ensure the safety of the participants.

Participants will also be encouraged to report any injuries that occur during the exercise sessions. With all injuries, a discussion will be held to determine whether removal is appropriate, however, in the case of any injuries that requires medical intervention, an individual's participation will be discontinued.

RANDOMIZATION AND BLINDING

Participants will be recruited to the study by the Co-Investigator [name] and the Chief Investigator [name]. All participants will go through an initial screening appointment and then a final decision regarding recruitment will be made after discussion between the study investigators. Following this, they will be randomised to either the intervention or control groups by [name] using the online "Sealed Envelope" software (www.sealedenvelope.com), which is the standard method of randomisation utilised for studies in this research department. The randomisation ratio will be 1:1 and the allocation

sequence will be generated by an algorithm within the online software, and as such, will be third party.

This study will be investigating the effects of an exercise intervention. Due to the nature of this intervention and the processes required to safely monitor the intervention group, blinding of participants or study investigators will not be possible. However, any research staff involved solely in data analysis will be blinded to the group that participants are allocated to. Neither those involved in data analysis, nor the study statistician will have contact with participants.

Maintenance of randomisation codes and procedures for breaking code

Blinding of participants and research staff is not possible in this study, therefore will not be used. Thus, there will not be any randomisation codes and no need to break a randomisation code. In the event of an SAE, the group in which the participant has been allocated to will be easily accessible from the study master file, which can be accessed by the Chief Investigator or any of the Co-Investigators.

TRIAL/STUDY MANAGEMENT

The trial will be managed by a single assigned project manager. There will not be a Trial Steering Committee, Management Group or Data Monitoring Committee for this.

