- failure to achieve minimum compliance with the exercise intervention

If a participant withdraws their consent after screening but before the first study visit, they may be replaced. Should a participant withdraw during or following the first study-visit, they will not be replaced, and instead, will be deemed to have dropped out of the study. As randomisation will occur immediately before the participant's first study visit, anyone who withdraws after randomisation will also be classed as a drop-out from the study.

For participants that are removed from the study, details of this decision will be documented in the CRF. The date and time of removal will be documented, as well as the reason for doing so (if provided). A decision to remove any participant that is made by the research team, will be discussed with the Chief Investigator and will require final agreement by them. We do not envisage any potential issues with abrupt withdrawal from the study and therefore, do not have measures to prevent any issues. Participants that are withdrawn will be advised to continue their care arrangements with their General Practitioner, and a letter will be sent to the General Practitioner informing them of the individual's participation in the study – in the same way as for all participants who complete the study.

Informed consent

All participants will provide written informed consent. The Informed Consent Form will be signed and dated by the participant before they enter the trial. The Investigator will explain the details of the trial and provide a Participant Information Sheet, ensuring that the participant has sufficient time to consider participating or not. The Investigator will answer any questions that the participant has concerning study participation.

Informed consent will be collected from each participant before they undergo any interventions (including physical examination and history taking) related to the study. One copy of this will be kept by the participant, one will be kept by the Investigator, and a third will be retained in the patient's hospital records.

Should there be any subsequent amendment to the final protocol, which might affect a participant's participation in the trial, continuing consent will be obtained using an amended Consent form which will be signed by the participant.

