A paper copy of the blood test results will be sent to the department. These, along with the rest of the screening information will be reviewed by a clinical member of the research team and discussed with the Chief Investigator, who will make the final decision regarding recruitment. Any abnormal results will be discussed with the prospective participant and their General Practitioner will be informed to ensure this is followed-up appropriately. If an individual is deemed to be suitable for recruitment into the study, they will be invited to attend their first study visit and a letter will be sent to their General Practitioner informing them of their involvement. Prior to the first study visit, the confirmed participant will be randomised into one of the following groups:

[figure not shown]
1. Intervention group
2. Control group

First study visit

The procedure for the first study visit will be identical for all participants, regardless of the group they have been randomised to. Participants will be asked to arrive at the clinical research facility between 0830 to 0900, after fasting from midnight the night before (water will be allowed). Upon arrival, they will have their body weight measured and BIA performed to provide an accurate measure of body composition.

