With these measures in place, we will endeavour to ensure that less than 10% of the data set will be missing. If this is achieved, the data will be analysed using standard statistical techniques as described above. However, if despite these measures there is greater than 10% missing data, this will be discussed directly with the support statistician and the procedure for dealing with this will then depend on the extent of data that is missing. Techniques such as imputation will be considered if required, however if analysis can be performed without the need for such techniques then this would be the preferred option.

If it is not possible to perform an IVGTT in a particular participant (e.g. due to difficulty obtaining vascular access), no data regarding the primary outcome will be collected for that participant. In this situation, data will still be collected for the remaining secondary outcomes during the first visit. Moreover, the participant will be permitted to participate in the 16-week intervention (or control) period and the second visit will be conducted, however without the repeat IVGTT. In order to ensure the target number of participants is reached, with regard to the primary outcome, an additional participant will be recruited for every participant that cannot complete the IVGTT.

Definition of populations analysed

Full Analysis set: All randomised participants, who participated in at least one HIIT session and for whom at least one post-baseline assessment of beta-cell function is available.

Per protocol set: All participants in the Full Analysis set who are deemed to have no major protocol violations that could interfere with the objectives of the study.

ADVERSE EVENTS

Definitions

An adverse event is any unfavourable and unintended sign, symptom, syndrome or illness that develops or worsens during the period of observation in the study.

An AE does include a / an:

1. exacerbation of a pre-existing illness.
2. increase in frequency or intensity of a pre-existing episodic event or condition.
3. condition detected or diagnosed after medicinal product administration even though it may have been present prior to the start of the study.
4. continuous persistent disease or symptoms present at baseline that worsen following the start of the study.

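### Randomising before the baseline visit lets unblinded staff make safety removals and run baseline tests with the arm known; randomise at the end of that visit

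*Protocol*

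**What the plan says.** **Order of events.** Under Trial / Study Treatment and Regimen, Screening: "Prior to the first study visit, the confirmed participant will be randomised into one of the following groups". The Participant Withdrawal section is more specific: "As randomisation will occur immediately before the participant's first study visit, anyone who withdraws after randomisation will also be classed as a drop-out". The first visit follows, with weight, bioimpedance, IVGTT, muscle ultrasound, questionnaires, EMG, one-repetition-maximum strength and CPET. Its procedure is the same in both groups, and home HIIT starts only afterwards (Intervention Period).

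**Blinding.** The Synopsis states: "Research staff in direct contact with participants will not be blinded". Randomization and Blinding adds that "blinding of participants or study investigators will not be possible". Only staff who work solely on the analysis of samples or data are blinded.

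**Removal at baseline.** Safety endpoints describes suitability for home exercise as assessed at initial screening and at baseline exercise testing, and continues: "If any concerns become apparent at this stage then the participant will be removed from the study on the basis of their safety". For the listed CPET signs, Stopping rules and discontinuation says: "If any of these were to occur during the CPET session then this will also be grounds for removal from the study".

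**Replacement.** Participant Withdrawal counts removal at the investigator's discretion as withdrawal, and does not replace anyone who withdraws during or after the first visit. Under Procedures for missing, unused and spurious data, a participant in whom the IVGTT cannot be done stays for the secondary outcomes without a repeat IVGTT, and "an additional participant will be recruited for every participant that cannot complete the IVGTT". The Full Analysis Set requires a post-baseline assessment of beta-cell function.

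**The concern.** Part of the eligibility decision, and all of the baseline measurement, happen after allocation. Three consequences follow.

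1. **Safety removals.** Screening offers a medical history, an ECG, blood tests and a light familiarisation ride, so the baseline CPET is the first maximal test. The ground for removal is any concern at all. Staff who apply it can know whether the person is about to start unsupervised HIIT or to carry on as usual, and their threshold may differ accordingly. Anyone removed has no final IVGTT and leaves the primary analysis.
2. **Secondary baselines.** VO2max, strength, EMG and ultrasound depend on effort, encouragement or operator judgement. A baseline shifted by knowledge of the arm carries into the comparison of change.
3. **Baseline IVGTT failures.** These participants have been randomised but can never contribute to the primary endpoint. The extra recruit is not directed to the depleted arm. This is a loss of precision and balance more than a source of bias.

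**Working it through.** The protocol has no power calculation and no failure rate, so there is no figure of its own to reproduce. The main check is the sequence of events. The arithmetic only shows scale.

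**Does anything at the first visit need the allocation?** No. The procedures are identical in both groups, HIIT begins after the visit, and the heart-rate target for HIIT is derived from that visit's CPET. The programme cannot be fully issued until the visit is over.

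**What becomes of each kind of baseline-visit failure?**

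| Event at first visit | Stays in trial? | Extra recruit? | In Full Analysis Set? |
|---|---|---|---|
| Removed on safety grounds at CPET | No | No | No (no post-baseline IVGTT) |
| IVGTT cannot be done | Yes, secondary outcomes | Yes, arm not specified | No (no repeat IVGTT) |

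Both losses come after randomisation under the present order. Neither would if randomisation closed the visit and those who fail were not randomised.

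**How likely is at least one?** Inputs: 20 participants, 1:1 (Synopsis). Assume that each participant independently has probability f of either event.

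P(at least one) = 1 − (1 − f)^20

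- f = 3%: 1 − 0.97^20 = 0.456
- f = 5%: 1 − 0.95^20 = 0.642
- f = 10%: 1 − 0.90^20 = 0.878

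**Unequal losses.** With 10 per arm, P(unequal) = 1 − Σ P(k of 10)^2, which is 0.54 at f = 5% and 0.69 at f = 10%.

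**Precision.** One loss is 1/10 = 10% of an arm. For a two-sample t-test (two-sided 0.05 and 80% power, both assumed here), the detectable difference is 1.33 SD with 10 and 10, 1.37 SD with 9 and 10, and 1.41 SD with 9 and 9. The precision cost of one or two losses is modest.

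**Selective removal.** If the lowest of 10 values on a normally distributed baseline measure were removed from one arm only, that arm's mean would rise by about 0.17 SD. This is an illustration; nothing in the protocol shows that it would happen.

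**Biased baseline.** Suppose knowledge of the arm lowers the baseline mean of one group by δ. The difference in change is then wrong by δ. With regression on baseline at slope b, the error is bδ, usually smaller but not zero.

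**Attendance after the fix.** 20/(1 − f), rounded up: 21 at 3%, 22 at 5% and 23 at 10%.

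**The case against.** The best defence is that the primary endpoint is well protected. It is an insulin area under the curve measured by ELISA, and staff working solely on sample analysis are blinded. That largely stands: the effort and operator argument concerns secondary outcomes. It does not cover removals, because a removed participant leaves the primary analysis however the assay is run.

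Several further points limit the concern:

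- Many of the CPET grounds are numerical, which narrows discretion. It remains for symptoms and for the general clause on concerns.
- Screening and the exclusion criteria, which are based on contraindications to CPET, should keep baseline removals few.
- Statistics, Methods provides a linear regression if baseline means differ. This is partial mitigation: it is triggered by an observed difference and cannot tell chance imbalance from bias.

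A reader might infer more than the text supports:

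- *Participants perform baseline tests knowing their arm.* The protocol does not say when they are told. It says only that contact staff are unblinded, and it provides nothing to conceal allocation during the visit.
- *IVGTT failures are excluded from the trial.* They stay for secondary outcomes, and an extra person is recruited. The example given, difficult vascular access, has no evident link to arm.
- *Enrolment concealment has failed.* The recruitment decision precedes randomisation, and third-party software generates the sequence.

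**Conclusion.** The order of events is a real weakness and should be fixed. Discretionary safety removals at the baseline visit can be made with the arm known, are not replaced, and are lost from the Full Analysis Set. Baselines of the effort- or operator-dependent secondary outcomes are open to the same influence. Baseline IVGTT failures add avoidable post-randomisation loss from the primary analysis, mainly at the expense of precision and balance.

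The size of any bias cannot be derived from the protocol. The 64% chance of at least one loss (46% to 88%) rests on an assumed 5% failure rate (3% to 10%), pools two kinds of failure that the protocol handles differently, and measures the chance of a loss, not of bias. The documents do not support calling the primary result invalid. The case for acting is that the present order gains nothing and that, with 20 participants, later analysis could not reliably repair arm-dependent removals.

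**What to change.** Randomise at the end of the first study visit, after the IVGTT, strength and EMG tests and CPET are complete and the suitability decision is recorded. Then issue the HIIT pack. No removal criterion changes.

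Amend three places together:

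- **Screening:** move the randomisation step to the end of the first visit.
- **Participant Withdrawal:** people who fail at, or withdraw during, the baseline visit are replaced before randomisation. Withdrawal after randomisation remains a drop-out.
- **Procedures for missing, unused and spurious data:** limit the extra-recruit rule to baseline failures before randomisation. State that randomised participants are not replaced for a missing final IVGTT.

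Case Report Forms allows the identity code to be allocated at randomisation. It should be allocated earlier, so that baseline samples can be labelled.

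**Cost.** A wording amendment, and about one to three more people at the baseline visit under the assumed rates. Secondary-outcome data from people whose IVGTT cannot be done would be given up, unless the sponsor chooses to randomise them for secondary outcomes only, outside the primary-analysis target. The change can apply to everyone not yet randomised. It does not address unblinded testing at the final visit or later exclusions for poor compliance.
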